Community health workers and healthcare staff will be recruited into the study via email. As indicate above, the CHWs are members of the study team. The healthcare staff will be members of UCR Health or CVFC for whom we have direct contact. The project coordinator, [name], will send an email following a script to all community health workers and healthcare staff involved in the study via partnering healthcare organization (e.g., UCR Health) inviting them to participate in a one-on-one interview (see *Appendix X. Recruitment of Community Health Workers and Healthcare Staff*). Because the Community Health Workers are members of the research team listed on the roster and we will already have the email addresses of healthcare staff members, we will already have their email addresses and will use thus reach out to those collaborating community health workers and healthcare staff members.

18. Compensation: Will participants be compensated for their time? Describe the methods, amount and schedule for payment. What will happen to compensation if participants chose to withdraw? If no compensation is being offered, please justify why.

(Max ¼ page)

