Group A - Grow Well. Our team collaborated with mothers and caregivers to adapt the Healthy Beginnings curriculum (<http://www.healthybeginnings.net.au>) for low-income Latinx immigrant families and communities. The curriculum focuses on healthy eating through education on nutritional content, parental and caregiver roles, and responsibilities for food preparation and family mealtimes. The intervention also encourages use of responsive feeding practices (i.e., responding to baby's hunger and fullness cues), as well as communication skills and conflict resolution strategies regarding baby's feeding. The original Healthy Beginnings curriculum includes material for mothers of infants 0 to 24 months. For the purposes of the pilot project, we will implement and evaluate material for infants 4 to 12 months (see *Appendix F. Adapted Healthy Beginning Modules 4 to 12 months*). The rationale for focusing on this age range is solid food introduction and transition to eating family meals occurs during this time. The intervention will be six months and include three components: 1) 30-45 minute monthly in-person delivery of material to mother and other caregivers; 2) 15-to-20-minute monthly phone call with mothers, and 3) being part of a WhatsApp group chat to receive weekly posts. Study team community health workers (CHWs) will deliver the intervention. All CHWs will participate in a training (in Spanish) on how to deliver the intervention prior to the start of the research.

In home sessions. For all in-home sessions, the CHWs will follow scripts. The scripts will provide instruction on delivering infant nutrition information, recommended infant feeding practices, and communication and conflict resolution strategies, and self-care practices for mothers and caregivers (see *Appendix G. Community Health Worker Scripts for In-home Sessions*). At the end of the in-home sessions, the CHW will work with the mothers and caregivers to set goals for infant care and feeding, communication strategies, and self care (see *Appendix H. Goal Setting*).

Phone calls. The CHWs will call (phone or video depending on participant preference) mothers one time per month of the intervention to check in on the goals and answer questions (see *Appendix G. Community Health Worker Scripts – refer to section for Phone Call Check ins with mother*). This call will occur two weeks after the in-home session and be approximately 15 to 20 minutes in length.

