participant's preference; each survey will last about 30-45 minutes. The survey will collect data on sociodemographic questions (e.g., income, education, language, mental health), infant feeding practices using the validated Infant Feeding Scale Questionnaire (Thompson et al., 2009), communication skills and conflict resolution strategies around feeding between the mother and other caregiver, and questions about breastfeeding, formula feeding, and family mealtimes (see *Appendix L. Pretest and Posttest Survey for Caregivers* and *Appendix M. Pretest and Posttest Survey for Mothers*). All participants (mothers and caregivers) will receive \$75 for completion of the pretest data collection and \$125 for completion of the posttest data collection. The purpose of an increased amount from baseline to follow-up is to compensate participants for the completion of the brief satisfaction surveys throughout the study and retain participants in the study over six months. (While only Group A participants will complete the brief satisfaction surveys, for purposes of equity all participants will receive \$125 at the end of the study.) In the final week of the study (week 24), study team members will administer the posttest surveys. The posttest survey will include the same questions as the pretest survey except it will not include the socio-demographic questions and will include a satisfaction survey. Only participants assigned to Group A – Grow Well will respond to the satisfaction survey questions. Participants can refuse to answer or skip any questions in either the pretest or posttest survey. If participants exit out of the study, their data will be removed from analysis.

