Anthropometric data collection. Anthropometric data will be collected at baseline and follow up. Because data will be collected at the CVFC, held the 2nd Saturday of the month, baseline data will be collected in week 2 of the intervention and follow up data in week 22. Trained medical students and CHW study team members will collect anthropometric data, weight, length, and body fat composition from infants at the beginning and end of the study period. We will collect infant weight using an infant scale, length using an infant measuring device that infants lay on, and body fat composition using fat calipers (see *Appendix N. Anthropometric Data Collection*). Mothers will be invited to bring their baby to the clinic for the purposes of data collection. However, if a mother is unable to bring their baby to the clinic, a study team member will collect data at the mother's home. Data collection will take approximately 10-15 minutes. [name] who is trained in infant anthropometric data collection will train study team members to collect and record these data prior to data collection. Participation in the study require infant anthropometric data collection. If participants exit out of the study, their infant's anthropometric data will be removed from analysis.

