Feasibility. After the completion of the implementation of the intervention, the study team will determine the feasibility of CHWs delivering the intervention in person with mothers and other caregivers present. We will conduct qualitative debriefing interviews with the CHWs (n=3) who implement the intervention, as well as with healthcare staff recruiting mothers into the study (n=3) (see *Appendix O. Community Health Workers and Healthcare Staff Interview Guide*). The debriefing interviews with CHWs will obtain information on the ease of delivering the intervention in-person with mothers and caregivers present, ease and utility of the phone check-in, the recruitment and retention of participants, and collection of infant anthropometric data. The debriefing interviews with healthcare staff will assess ease of recruiting mothers in a healthcare setting and communicating contact information with study team members. These interviews will be 30-60 minutes, audio recorded, and analyzed using rapid analytic techniques of template and matrix analysis. Study team members will listen to the audio recordings, complete a summary template, and use a matrix to identify themes. Participants will receive a \$25 gift card for their time.

Fidelity. Throughout the delivery of the intervention, the study team will also determine fidelity or how well the delivery of the intervention adheres to instructional procedures. To assess fidelity, research assistants (RAs) will participate in 30% of the in-person sessions and phone calls with the CHWs as they deliver the curriculum to mothers and caregivers. For the in-home sessions, RAs will join the sessions virtually via Zoom on tablets that CHWs will bring with them to the visit. For the phone calls, the RAs will join the call with the CHWs and mothers. For both in-person sessions and phone calls, the RAs will use a checklist to assess how well the CHWs follow the instructional scripts on material to share and activities to complete (see *Appendix P. Fidelity Checklist- Research Assistant*).

Additionally, the CHWs will use a checklist to assess their perceived fidelity to the program, which they will complete after each in-home session and phone call check in (see *Appendix Q*. Fidelity Checklist- Community Health Worker).

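### On the protocol's own timetable the clinic baseline infant measurements follow allocation, against its stated order; secondarily, nothing shown stops a CHW from assessing a family she coached.

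*Protocol*

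**What the plan says.** **Order of events (section 20a).** The Procedures text has randomisation take place once baseline data are in. The Group B paragraph has packets mailed to control mothers in the first week of study months 1, 3 and 5, with a CHW call in the same weeks to confirm receipt. The Data Collection paragraph ties week 1 to the start of the calendar month and puts the pretest survey in week 1, before the trial starts. The anthropometry paragraph puts the baseline measurement in week 2 of the intervention, because the clinic is held on the second Saturday of the month. Infant anthropometry is listed in section 20a among the preliminary-efficacy outcomes.

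**Who assesses.** On delivery, section 20a says "Study team community health workers (CHWs) will deliver the intervention". On infant measurement it says "Trained medical students and CHW study team members will collect anthropometric data, weight, length, and body fat composition from infants", and "if a mother is unable to bring their baby to the clinic, a study team member will collect data" at her home. On the survey it says "In the final week of the study (week 24), study team members will administer the posttest surveys". Section 17 states "As indicate above, the CHWs are members of the study team", so that term includes them. Section 16b gives CHWs as a group both data collection and delivery. The Feasibility paragraph plans "qualitative debriefing interviews with the CHWs (n=3) who implement the intervention", and lists infant anthropometry among the topics of those interviews.

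The posttest repeats the pretest "except it will not include the socio-demographic questions and will include a satisfaction survey". Only Group A participants answer that part: "Grow Well will respond to the satisfaction survey questions".

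**The concern.** A baseline value should be fixed before anyone knows the allocation. Only then does a baseline difference between arms reflect chance, and only then is the value clean to adjust for or subtract. Skinfold calipers depend on the operator, so a measurer who knows the group could influence the reading. With 15 infants per arm there is little room to absorb such an influence. A results paper that relied on the Procedures text would also describe the measurement order wrongly.

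The second strand concerns follow-up. The survey is given orally and relies on self-report. A mother interviewed by the CHW who set feeding goals with her may lean towards the taught answers, and a control mother has no such relationship. If that happened, the survey comparison would plausibly favour Grow Well. For calipers the direction is unknown.

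**Working it through.** **1. Timing check.** Inputs, all from section 20a: enrolment cohorts start in the first week of each month from April to August 2023; week 1 begins with the calendar month; control packets and calls fall in the first week of month 1; the clinic is on the second Saturday.

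A second Saturday always falls on day 8 to 14 of a month, and week 1 is day 1 to 7.

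| Cohort (2023) | Second Saturday | Days after week 1 ends |
|---|---|---|
| April | 8 | 8 − 7 = 1 |
| May | 13 | 13 − 7 = 6 |
| June | 10 | 10 − 7 = 3 |
| July | 8 | 8 − 7 = 1 |
| August | 12 | 12 − 7 = 5 |

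Control material can go out in week 1 only if allocation is already known. The clinic is later in every cohort. Two readings of the randomisation sentence are open:

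- Baseline data includes anthropometry. The sentence then contradicts the Group B and anthropometry paragraphs.
- Baseline data means the survey only. The sentence then stands, but anthropometry is a post-allocation measurement that is labelled baseline.

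On either reading the clinic values follow allocation. The consent text in section 23a fits this, since it allows a Group A home session to be the first in-person event. The week-1 survey can still precede allocation within that week.

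**2. Contact between CHW and family (section 20a).**

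- Grow Well mother: 6 sessions × 30–45 min + 6 calls × 15–20 min = 180–270 + 90–120 = 270–390 min over 12 contacts.
- Control mother: 3 receipt calls.
- Grow Well caregiver: 6 × 30–45 = 180–270 min. Control caregiver: none scheduled.

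**3. Illustration of assessor bias. Every value except 15 per arm is assumed.** The protocol states no test, alpha or interviewer effect. Take a two-sided 5% t-test with 28 degrees of freedom and no true effect. Suppose that being assessed by one's own CHW shifts a family's survey score by b SD, with b = 0.2, 0.3 or 0.5. Standard error of the difference = √(2/15) = 0.365 SD. Mean shift = share of Grow Well families so assessed × b. Noncentrality = mean shift / 0.365.

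| Share assessed by own CHW | b = 0.2 | b = 0.3 | b = 0.5 |
|---|---|---|---|
| 0 | 5.0% | 5.0% | 5.0% |
| 1/3 (mean shift 0.067, 0.10, 0.167) | 5.4% | 5.8% | 7.3% |
| 1 (mean shift 0.2, 0.3, 0.5) | 8.3% | 12.5% | 26.2% |

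Entries are false-positive rates. The share of one third is what would arise if the 3 implementing CHWs did all the assessing and were assigned without regard to who had coached whom.

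**The case against.** **On timing.** The gap after week 1 is 1 to 6 days. Weight and length are read from instruments, and one mailed packet or one session is unlikely to change them in days. The hypothesis in section 12 names feeding knowledge and practices, not anthropometry. All of this limits the harm, and leaves observer influence on calipers as the main risk. It does not remove the conflict, because section 20a does list anthropometry as an efficacy outcome.

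**On assessors.** A reader might infer that CHWs are planned to assess their own families. The documents do not say so:

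- Medical students share the measuring, and no CHW is named as the posttest interviewer.
- Section 12 of the form's recruitment rules is not needed to see the wider pool: section 17 names more CHWs than the 3 who are to be debriefed as implementers, and section 6 mentions bilingual research assistants.
- For Purépecha speakers, section 15 appears to give data collection and intervention material to different translators. The data-collection translator also handles the brief satisfaction surveys, which only Group A completes, so she cannot be assumed masked.
- The roster, training agendas, survey forms and measurement form (Appendices A, A1, L, M and N) are not shown and may settle assignment and item order. If the satisfaction items already come last, the outcome answers are recorded before those items reveal the group.

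These objections stand, and they reduce the assessor strand to a cheap improvement. Section 16b also presents CHW involvement as a deliberate means of building trust, which a remedy should respect.

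A bar on anyone who observed a family for fidelity would go too far. Research assistants join 30% of contacts: 15 families × 12 contacts = 180, and 0.30 × 180 = 54, or 54/15 = 3.6 per family. Every Grow Well family may have been observed by one of them.

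**Conclusion.** The timing conflict is established from the text. In all five cohorts, baseline anthropometry at the clinic falls 1 to 6 days after the week by which allocation must be known. This rests on reading month 1 of the study as starting with week 1, which is how section 20a sets out the calendar. It applies to clinic weight, length and caliper values. The timing of home measurements is not separately fixed, and the pretest survey is unaffected.

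The assessor point holds only as a gap: overlap between coaching and assessing is permitted, not planned. The size of any bias is unknown. A reader might take the 26.2% in the illustration as the trial's error rate, but it needs every Grow Well family to be assessed by its own CHW and the largest assumed shift. If no family is, this source adds nothing. The effect is small unless CHWs mostly assess their own families, and no passage says that they will.

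This is a 30-triad pilot with feasibility and acceptability aims, which limits the consequence. Both changes are nevertheless worth making, because the preliminary-efficacy comparison is a stated aim.

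**What to change.** **Main change (section 20a).** Reconcile the randomisation sentence, the Group B schedule and the anthropometry paragraph so that baseline anthropometry is complete before randomisation. Either of two routes would do:

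- Randomise, and start month-1 material in both arms, after the second-Saturday clinic. This costs a scheduling shift of one to two weeks, and the 24-week count must be restated to match.
- Use the home-measurement option already in the protocol before randomisation. This costs staff time and travel.

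If neither is possible, say that the measurement is taken after allocation, and do not describe or use it as a pre-randomisation baseline.

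**Secondary change (section 20a, survey and anthropometry paragraphs).** Assign the posttest survey and follow-up anthropometry, at clinic or home, to existing team members who did not deliver to that family. Examples are medical students for the measurements, or CHWs who worked with other families. Where feasible, do not tell them the group. Ask the Group A satisfaction items after all outcome items. CHWs keep their recruitment and delivery roles.

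The costs are some scheduling effort and a less familiar interviewer. Masking will be incomplete, and participants know their group, so self-report bias is reduced and not removed. That the existing roster is large enough, with the languages needed, is an assumption, since the roster is not shown.

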- Using a pilot randomized control trial with 30 mother-infant-caregiver triad (15 intervention, 15 control) determine the feasibility, acceptability, and preliminary efficacy of the adapted intervention compared to the original intervention. We hypothesize that the adapted intervention will be feasible, acceptable to study participants, and efficacious in addressing feeding styles and practices and caregivers' role in infant feeding.

We anticipate that the intervention will be feasible to deliver and acceptable to mothers and caregivers, and that the mother—infant-caregiver triads randomized to intervention with the adapted Healthy Beginnings curriculum compared to the treatment as usual control group will demonstrate greater improvements in outcomes (i.e., infant feeding knowledge and use of recommended feeding practices) after 6 months compared to the control group.

III – Study Design and Methodology

13. Study Timelines

Estimated start date for involvement of participants: February 1, 2023 or upon approval of the IRB protocol.

Estimated completion date for the involvement of participants: Feb. 28, 2024

14. Location of Research

a) Where will this study take place? If there is an online component, provide details.

(Max ¼ page)

The research will be carried out in Inland Southern California, specifically communities of the Coachella Valley and surrounding area. The PI, [name] and Co-Investigator [name], along with graduate and undergraduate research assistants are located at UCR. Co-I, [name], and research coordinator/assistant, [name], is located at Brown University. Community Investigator, [name], is located in the Coachella Valley. All research takes place at UCR. The research will primarily engage Latinx and Indigenous Mexican (e.g., Purépecha) communities in Inland southern California.

b) Is this a collaborative or multi-site study? Yes No

- Collaborative or cooperative studies involve investigators from two or more institutions working together to conduct a research project. Different research activities can occur at different sites or the study can be a single-site study that involves personnel from multiple institutions.
- Multi-site studies use the same research procedures outlined in a single protocol that is carried out at multiple institutions (e.g., a clinical trial where participants will be enrolled at each participating site, or an educational intervention implemented at each participating site).

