Gift cards will be shared with participants depending on how they select delivery on the consent form, thus either by email, mail, or delivered to home. All consent forms offer these options and participants can select the best option for them. If participants have begun the research and then chose to withdraw, they will still be provided the compensation to thank them for their interest and time.

19. Reimbursement: Will participants personally incur any expenses as a result of participation (e.g., fuel, missed work)? If no reimbursement is being offered, please justify why.

(Max ¼ page)

Participants will not incur any expenses because of participation as events will occur online via Zoom or phone, in their community, or when they access healthcare services.

20. Procedures

a) Describe how human participants will be involved in the research. If there is to be an intervention or interaction with the participants, describe what the researcher and participants will do, who will conduct the procedures, where and when the procedures will take place, how frequently, for how long, what equipment will be used, etc.

(Max ½ page)

Human subjects will be involved in the research via the pretest and posttest survey, brief satisfaction surveys, anthropometric body measurements, and one-one-one interviews. The research involves data collection around the implementation of an infant nutrition education curriculum (i.e., the adapted version of Healthy Beginnings). This is an intervention study and a pilot randomized control trial (RCT) with an intervention arm and a control group to determine: 1) the preliminary efficacy of the adapted intervention on mothers' and caregivers' infant feeding knowledge, use of recommended feeding practices, and infant anthropometric measurement outcomes 2) the feasibility of implementing the intervention and its acceptability among mothers and caregivers, and 3) the feasibility of collecting infant anthropometric data.

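### The only stated way of judging feasibility is six debriefing interviews, so the conclusion need not reflect how many triads enrolled, attended or stayed

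*Protocol*

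**What the plan says.** Item 12, Aim 1, sets the pilot to "determine the feasibility, acceptability, and preliminary efficacy of the adapted intervention compared to the original intervention", and the hypothesis there expects the programme to be feasible. The opening of item 20(a) lists preliminary efficacy first and then "2) the feasibility of implementing the intervention and its acceptability among mothers and caregivers, and 3) the feasibility of collecting infant anthropometric data".

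The method is in item 20(a) under its own Feasibility heading. The question posed is whether CHWs can deliver in person with mother and caregiver both there. The means is: "We will conduct qualitative debriefing interviews with the CHWs (n=3) who implement the intervention", with a further three interviews of healthcare staff who recruited. CHWs are asked about ease of delivery, the phone check-ins, recruitment and retention, and collection of infant measurements. Healthcare staff are asked about ease of recruiting and of passing on contact details. The analysis is a summary template and a theme matrix. Items 15 and 18 describe the same interviews as the feasibility assessment.

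On the interviewees, item 17 says that "the CHWs are members of the study team". Item 16(b) has CHWs recruiting, delivering and leading data collection and analysis, and item 20(a) has CHW team members among those who measure the infants.

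On participants who leave, item 20(a) says: "If participants exit out of the study, their data will be removed from analysis". It says the same of infant measurements. Item 25 goes further: after a confirmed withdrawal, all of that participant's data are destroyed and kept out of analyses and deliverables.

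**The concern.** Two of the feasibility questions are matters of fact that can be counted: how often a home session took place with both adults present, and how many infants were measured at both times. The stated method asks instead how easy these tasks seemed to the people who carried them out. A CHW can truthfully find delivery easy in the sessions that took place while many planned sessions never happened. An interview about ease does not show the second fact.

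The three CHWs would also be assessing their own recruitment, delivery and measurement. At stake is whether a stated aim of the pilot is reported with rates that a reader can use, or only as themes.

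**Working it through.** No stated figure is in dispute. The protocol gives no recruitment, attendance or retention rate to reproduce. The check is to set each feasibility question beside its stated source, and then see what counts could provide.

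**1. Stated source for each question (Protocol, item 20(a))**

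| Question | Stated feasibility source | Countable as |
|---|---|---|
| Recruiting mothers | Staff and CHW interviews | Enrolled / eligible |
| In-person delivery with both adults present | CHW interviews | Sessions with both present, out of 6 per Group A triad |
| Phone check-ins | CHW interviews | Calls completed, out of 6 per Group A triad |
| Retention | CHW interviews | Week-24 posttests completed, by arm |
| Infant measurements | CHW interviews | Infants measured at both times |

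**2. Do neighbouring measures fill the gap?** Fidelity has its own heading. Research assistants observe 30% of sessions and calls to check adherence to the script, and CHWs fill in a checklist "which they will complete after each in-home session and phone call check in". The checklist could yield delivery counts as a by-product, but the protocol assigns it to perceived fidelity, and its content (Appendix Q) is not shown. Satisfaction, also under its own heading, concerns Group A participants' views. Neither is made a feasibility measure, and both draw on contacts that took place or on people who responded.

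**3. Size of the two bases**

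- Interviewees: 3 + 3 = 6.
- Triads: 15 + 15 = 30.
- Planned Group A home sessions: 15 × 6 = 90. Planned Group A calls: 15 × 6 = 90.
- Sessions in the fidelity sample: 0.30 × 90 = 27, checked for script adherence and not for attendance.

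**4. Precision that counts would give.** Exact (Clopper-Pearson) 95% limits for x out of n are the 0.025 quantile of Beta(x, n − x + 1) and the 0.975 quantile of Beta(x + 1, n − x). The numerators below are assumed, because the protocol states none.

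| Assumed count | Proportion | Exact 95% CI |
|---|---|---|
| 21/30 triads | 70% | 51% to 85% |
| 24/30 triads | 80% | 61% to 92% |
| 27/30 triads | 90% | 73% to 98% |
| 12/15 in Group A | 80% | 52% to 96% |

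These intervals are wide, but each describes what happened to the triads.

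**The case against.** The strongest reply is that this is an ethics application. Item 20(a) asks, within half a page, how people will be involved. Interviews must be listed because CHWs and staff become subjects, whereas tabulating attendance involves no contact and could go unmentioned. That stands in part. The text never says that counts are excluded, so a reader who infers that no number will enter the judgement, or that the team could call the programme feasible whatever share stayed, goes beyond it. What remains is that the paragraph names an instrument, a sample and an analysis for determining feasibility, and no rate is among them.

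Other tempting readings also fail:

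- **All six are deliverers and study insiders.** Three are recruiting healthcare staff. Item 17 shows one UCR Health staff member on the project roster; the staff to be interviewed are not identified.
- **Feasibility is the leading aim.** It comes first in item 12, but efficacy comes first in item 20(a).
- **Retention cannot be counted because leavers are removed.** Removing their data does not prevent counting that they left, and item 26(c) keeps tracking files until the data are collected and analysed.
- **Progression thresholds are missing.** These are commonly left to an SAP, which is not shown, and the protocol mentions no follow-on trial.

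The objection is also right that counting is not entirely free. No log of screening outcomes is described, the checklist may not record who attended, and the destruction promise in item 25 has to be respected.

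**Conclusion.** The point holds as a weakness in a method the protocol itself fixes. Feasibility is a stated aim, six interviews are the only stated means of determining it, and three of the six interviewees are study team members commenting on their own work. The conclusion as written need not reflect enrolment, attendance, retention or measurement completeness, all of which can be counted.

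The word *only* describes what the protocol states; it does not show that the team will ignore counts. It rests on the text shown, without the appendices or an SAP. The size is the difference between themes from six people and proportions on 30 triads (15 for delivery). The intervals above are illustrations and do not measure an error in the plan. The change is worth making because it is small and bears directly on a stated aim.

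**What to change.** In item 20(a), Feasibility, make these the main measures, with exact 95% CIs for the proportions, and count everyone randomised, including those who leave:

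- triads enrolled out of those eligible (this one has the eligible as its denominator);
- home sessions held with both mother and caregiver present, out of 6 per Group A triad;
- calls completed, out of 6 per Group A triad;
- week-24 posttest completion, by arm;
- infants measured at both times, out of all infants in randomised triads.

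For sessions and calls, summarise by triad, for example the number of the 15 triads reaching each total. An exact interval on the pooled 90 would treat contacts within a triad as independent. Keep the six interviews, to explain the rates.

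State that an aggregate, non-identifying count of withdrawals by arm is kept. Reconcile this with the removal text in item 20(a) and the destruction text in item 25, including whether sessions and measurements of a withdrawn triad may still be counted in aggregate. Progression values can be left to the SAP.

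The cost is one paragraph, a line on withdrawals and a short tabulation, with no added visits. The session and call checklist must record who attended, and screening outcomes must be logged if they are not already. The downside is that the feasibility result may look less favourable than interviews alone would suggest.
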